Study Protocol and Statistical Analysis Plan

Clinicaltrials.gov ID: NCT05178979

Unique Protocol ID: K01MH121663-01A1

Secondary IDs: 1K01MH121663-01A1 [U.S. NIH Grant/Contract Award Number]

Title: A Gender Transformative Implementation Strategy With Providers to

Improve HIV Outcomes in Uganda

Protocol date: 11 July 2023 (final version date of approved IRB protocol)

Pls: [name]

Contact PI: [name], BC, [contact]

Contents

Inclusion criteria	3
Recruitment & Sampling	3
Data collection	4
Questionnaires	4
Process Data	5
Data management	6
Qualitative data	6
Quantitative data	6
Data safety monitoring plan	7
Adverse events	7
Training of the RAs/Facilitators	8
Training of research assistants	8
Training of intervention facilitators	8
Statistical Analysis Plan	9

Inclusion criteria

Provider cohort for training intervention, assessment, and exit focus groups (intervention trial). We will recruit providers for participation in our intervention trial for the provider training from the two selected clinics. The goal is to recruit the entire population of providers at each of the two clinics, which is approximately 20-35 providers per clinic (Luwero Hospital, Mityana Hospital, Kalagala HCIV and Namayumba HCIV) for participation. This cohort will include all HIV care providers at the 4 selected clinics, including: medical officers, clinical officers, HIV nurses, midwife, linkage facilitators, and counselors. These participants will be 18 years of age or older and fluent in English or Luganda.

Patient cohort assessment (intervention trial). In addition to the assessment of the cohort of ~80-140 HIV providers, we will obtain additional data on the impact of the provider training on patient outcomes including quality of care, patient satisfaction, clinic attendance, ART adherence, and viral load (from patient clinic records) by assessing 240 (60 per treatment facility, gender balanced) purposively sampled patients at baseline, 6-, and 12-month follow-up.

Eligibility includes:

- 1. HIV-infected;
- 2. enrolled in care at the clinic of recruitment;
- 3. pre-ART (newly diagnosed) or newly initiated on ART (within 1 year) or struggling with treatment adherence, defined in two ways:
 - a. most recent viral load results unsuppressed as assessed through clinic records
 - or self-reported non-adherence as by the Adult AIDS Clinical Trials Group (AACTG) scale 4-day adherence recall questions. This scale has demonstrated good construct validity in Uganda and strong correlations with viral load;
- 4. 18 years of age or an emancipated minor;
- 5. fluent in Luganda or English.

Recruitment & Sampling

Provider cohort for training intervention, assessment, and exit focus groups (intervention trial). Once research staff are trained and our two clinics have been randomly assigned as intervention or control arm, we will recruit providers for participation in our intervention trial for the provider training. The goal is to recruit the entire population of providers at each of the four clinics, which is approximately 20-35 providers per clinic (Luwero Hospital, Mityana Hospital, Kalagala HCIV, and Namayumba HCIV) for participation; approximately 35 at each hospital and 25 at each HCIV (total: 80-140). With support from Mildmay Uganda (see Letter of Support), we will generate support for the training first in the broader Health Districts (with medical superintendents and District Health Officers) through in-person meetings and garnering their feedback on the intervention through invitations to serve on/make recommendations for a "Training Steering Committee." After District support is attained, we will then conduct facility mobilization with an inperson presentation of the goals research study at each of the four clinics. Eligibility for providers includes being an HIV care provider at one of the four selected clinics. After the larger facility

mobilization meeting, the research assistant will meet one-on-one with HIV providers to individually inform them of the study, allow them to ask any questions in a private space, and obtain written informed consent. Though we aim to recruit all HIV providers at each clinic for participation, any provider can decline to participate. The informed consent process will include consent for both participation in the provider training, baseline, 6- and 12-month assessments, and an exit focus group. To mask the randomization of intervention and control, we will consent participants for participation in all aspects of the training.

Patient cohort assessment (intervention trial). In addition to the assessment of the cohort of ~140 HIV providers, we will obtain additional data on the impact of the provider training on patient outcomes including quality of care, patient satisfaction, clinic attendance, ART adherence, and viral load (from patient clinic records) by assessing 240 (60 per clinic, gender balanced) purposively sampled patients at baseline, 6- and 12-month follow-up. Patients will be non-randomly approached when presenting to care by a Research Assistant based on a review of clinic records. After being referred by a clinician, our research assistant will inform individuals of the study and assess eligibility using an eligibility screening tool. No identifying information will be recorded during the eligibility screening. If eligibility is met and the patient would like to participate, the research assistant will obtain written informed consent and collect patients' contact information (for follow-up reminders) and conduct the baseline questionnaire in the clinic or another agreed upon location.

Data collection Questionnaires

For the provider cohorts randomized to the Intervention clinics, the chronological activities include: enrollment; baseline interview immediately after enrollment; participation in ~21 hours of intervention content; follow-up assessments at 6-months and 12-months follow-up; one exit focus group post-intervention. Each data collection activity and its duration is detailed below:

- Baseline provider assessment (for all provider participants). After the informed consent process a one-on-one interview (~25 minutes) using a computerized structured questionnaire in the clinic or another agreed upon location will be conducted with providers at both clinics. The questionnaire will collect demographic information and measures to assess provider outcomes. The total duration of participation for the baseline survey is approximately 25 minutes.
- 6-, and 12-, month follow-up provider assessments (all provider participants). Research Assistants will conduct the 2 follow up interviews using an individual structured interviewer-administered computer-based interview in the clinic or another agreed upon location for patient and providers. Providers have the option to complete these assessments over the telephone only if they have transferred to working at another clinic and cannot be reached in person. The follow-up questionnaires will serve as a measure of intervention effects on provider's gender equitable attitudes and gender awareness and other related constructs (see Measures). This questionnaire is approximately 25 minutes per time point. Across the 2 assessments, the total duration for survey participation is approximately 50 minutes.

For the patient cohort (n=240) enrolled in the intervention and control clinics. To assess the effect of the provider training on patient-level outcomes, we will assess change overtime in patient outcomes in a cohort of HIV patients enrolled at the 2 clinics. These patients do not receive any intervention, but will participate in an assessment across 3 time-points (following the same schedule as the provider assessment). They will also agree to a review and data extraction of health information from of their HIV clinic records at each time point.

- Baseline patient assessment (all patient participants). HIV patients referred to the study and interested in participating will first answer a brief set of questions to assess enrollment. No data will be recorded at this time. If eligible and interested, we will obtain written informed consent before continuing with the baseline questionnaire. Using a computerized structured questionnaire, a research assistant will conduct the survey in the clinic or another agreed upon location at both clinics. The questionnaire will collect demographic information and measures to assess patient outcomes related to HIV care engagement (e.g., clinic attendance, medication adherence, patient satisfaction). Data will also be extracted at this time and directly entered into the computerized survey from patient clinic records (e.g., treatment regiment, CD4 count, viral load). Total duration of baseline interview is approximately 60 minutes.
- 6- and 12-month follow-up patient assessments (all patient participants). Patients at both clinics will complete a follow-up assessments at 4 time points, specifically 6 and 12-months post-baseline. In a private space in the clinic or another agreed upon location, an interviewer will administer a structured questionnaire entered in CAPI software. Follow-up assessments may be administered via telephone for participants not returning to the clinic (incentives delivered elsewhere). At each time point, information will again be reviewed and extracted from clinic records and entered into CAPI software. Across all 2 assessments, the total duration for survey participation is approximately 90 minutes (~45 minutes per assessment). Patient participation will end after the completion of the 12-month follow-up survey.

Process Data

Exit interviews with facilitators and key-stakeholders (post-intervention). Semi-structured qualitative interviews will be held with the 2 trainers (intervention facilitators), any provider not able to attend focus groups, as well as with 2-4 Mildmay leaders in charge of the integration of courses into Mildmay's training programs to assess barriers and facilitators to the implementation and future adoption of the training and maintenance sessions. See Table 3 for more detail on the CFIR constructs explored through these interviews. An audio-recorded, one-on-one semi-structured interview will be conducted in a private setting by one of the PIs or research staff. After the completion of the key-informant interview, the key informants' involvement in the study will end (total participation approximately 15-30 minutes).

Exit focus groups with providers (post-intervention). We will conduct approximately 8 additional exit focus groups with HIV providers participating in the training (6-8 provider per group) or until saturation is reached. We will purposively sample from each of the intervention health centers and include health workers and lay workers in separate groups. The purpose of these focus groups are to assess the perceived acceptability, feasibility, barriers to

implementation/adoption and other measures of implementation (see Table 1) among providers who participated in the training. The different constructs and their definition measured through focus groups mapped onto the CFIR framework are highlighted in Table 1.

Data collection to assess intervention fidelity. To assess fidelity, each group training session will be observed by staff or [name] with a checklist to assess 5 implementation fidelity dimensions: adherence, quality of delivery, program component differentiation, intervention exposure, participant responsiveness. We will observe ~5 randomly selected maintenance sessions (for rapid feedback). At the completion of the study, randomly selected maintenance transcripts (20%) will be qualitatively analyzed.

Table 1. CFIR domains and constructs explored as barriers and facilitators to the implementation and adoption of the intervention

CFIR Domain and constructs	Sample*	
CFIR Domain: Intervention characteristics		
Intervention source: Perception of key stakeholders about whether the intervention was externally or internally developed	Trainers, Stakeholders	
Complexity/barriers: Perceived difficulty of/barriers to implementation/application of content into clinical care	Trainers, Providers Stakeholders	
Appropriateness: The perceived fit of the intervention for the setting and to improve care quality and patient outcomes	Trainers, Providers Stakeholders	
CFIR Domain: Outer setting		
Patient needs: The extent to which patients' gendered barriers and facilitators to care are accurately known and prioritized	Trainers, Providers Stakeholders	
CFIR Domain: Inner setting		
Relative Priority: Perceived importance of implementation within the clinic and broader health system	Trainers, Providers Stakeholders	
Culture: Organizational norms, values, and basic assumptions specific to: a) innovations in care and b) gender equity	Trainers, Providers, Stakeholders	
CFIR Domain: Individual characteristics		
Knowledge and beliefs about the intervention: Attitudes towards and value placed on the intervention, including perceptions on acceptability (satisfaction with intervention) and feasibility (can intervention be carried out within clinic/broadly)	Trainers, Providers, Stakeholders	
Self-efficacy: Beliefs in own ability to execute implementation goals (trainers) and training content (providers)	Trainers, Providers	
Other personal attributes: Gender, age, and other traits	Trainers, Providers	

^{*}Data collection methods = Providers: focus group discussions, Trainers: in-depth interviews; Stakeholders: key informant interviews

Data management

Qualitative data

Audio recordings of all qualitative data will be transferred to a password protected computer. All focus group discussions, observations, key informant interviews, and qualitative exit interviews will be transcribed and translated into English and entered into a software analysis system (Atlas.ti). Electronic audio recordings of intervention sessions will be transcribed within 6 months of the session and the audio recordings will be destroyed once the information from the recordings is written down and double-checked for accuracy.

Quantitative data

Data for the baseline, 6- and 12-month follow-up questionnaires will be entered in real-time while the interviewers are conducting the interviewer-administered CAPI questionnaires (using

KoboCollect software). Using the KoboCollect system also eliminates the possibility of any out of range responses and therefore, data cleaning is not necessary. Data collected using Kobo is easily exported into R, SPSS, and other statistical programs for analysis. A research assistant will extract data form medical charts and enter it into a database identified only by study ID number. Clinical record data will be double entered by the research assistant into this same data file upon receipt. The double entered data will be checked and any discrepancies will be corrected by double checking the clinic records, and by comparisons with the laboratory report.

Data safety monitoring plan

The proposed study will conform to rigorous monitoring procedures, standardized reporting of adverse events using Event Report Forms, and regular review of the study by the Principal Investigators, Drs. [name] and [name]. [name] will have primary responsibility for the overall conduct of the study with oversight from Drs. [name] and [name], including the safety of human subjects. With the assistance of research staff, the Pls will ensure appropriate: (1) conduct of the informed consent process (e.g., that informed consent is obtained before proceeding with study procedures and properly stored), (2) enrollment of study subjects, (3) collection and analysis of data, (4) implementation of study procedures to ensure consistent monitoring of subjects for possible adverse events, (5) review of adverse events and reporting to the IRB, and (6) maintenance of the privacy and confidentiality of study subjects.

Drs. [name] and [name] will be responsible for meeting with the research team on a regular basis (either in person or by conference call) to review the progress of the study and address any human subject issues that occur. These discussions may involve adverse event prevention measures, recruitment of appropriate study subjects, research staff training on protection of human subjects, as well as occurrence of adverse events, unexpected incidents, or protocol problems. [name] will meet with the research assistants regularly to go over the progress of the study and communicate any issues or adverse events to the mentorship team. The research assistants will compile reports on this information and submit them to the Principal Investigator for review. Drs. [name] and [name] will present this information to Co-Investigators as needed to troubleshoot any issues and seek guidance in decision-making.

Adverse events

The study is of minimal risk and therefore no serious anticipated events are expected. Serious unanticipated events will be reported within 48 hours to the Makerere School of Public Health and University of Texas at San Antonio IRBs, the co-investigators listed on the protocol, and NIH. We expect the risk of adverse events resulting from participation in the intervention to be low. Further, we have developed procedures to reduce any adverse events and closely monitor participants in the provider training intervention. The implementation of these procedures will ensure any unanticipated adverse events are identified and addressed immediately (see "Protection of Human Subjects" section) for more details.

The Principal Investigators will conduct a review of all adverse events (serious and non-serious) every month during a scheduled meeting and keep a log of all events. They will evaluate the frequency and severity of the adverse event(s) and, in conjunction with the Makerere School of Public Health and University of Texas at San Antonio IRBs, determine if modifications to the protocol or consent forms are required. A report to the Makerere and University of Texas at San Antonio IRBs will be made when re-approval for the protocol is sought on a yearly basis, or more frequently if deemed necessary by the Principal Investigators and Co-Investigators based on the number and severity of adverse events. The summary will include the number of participants enrolled in the study and a summary of the adverse events to date (including relation to study and severity).

The Principal Investigators, in conjunction with the Makerere School of Public Health and University of Texas at San Antonio IRBs, will be responsible for monitoring the data and conducting performance safety reviews at a minimum of every 3 months. The Principal Investigators will present this data to the full-team of Co-Investigators for guidance at bi-annual team meetings. The Principal Investigators, Makerere IRB, and the University of Texas at San Antonio IRB have the authority to stop or modify the study at any time. During the review process, the Principal Investigators will monitor and evaluate whether the study should continue unchanged, require modification, or close to enrollment. Discussions will be brought to the larger team of mentors as needed.

Training of the RAs/Facilitators Training of research assistants

To collect baseline and follow-up interview data for the intervention trial experienced research assistants/interviewers will be hired for the purposes of the study. These individuals will be trained in the study procedures by one or more of the investigators. The two-day training will cover the detailed standard-operating-procedures (SOP) as relevant to the role of research assistants. Procedures covered will include the schedule of data collection, procedures for contacting participants, storage of hard copies, storage and exporting of electronic data, and procedures related to obtaining informed consent. Safeguards to protect human subjects and reporting of adverse events will also be covered. Finally, the training will cover the objectives and content of the study and the tools. Mock interviews will be conducted by the research team to further get acquainted with the study tools during the training. The training will help the research assistants to master the data collection tools. Clinic staff will also be oriented to the study and the study procedures by the investigators.

Training of intervention facilitators

Group facilitators experienced in the delivery of behavioral interventions and Mildmay Expert Trainers who will deliver the intervention will undergo a 5-day curriculum-based training of the intervention content using role playing and simulated group discussions led by [name] with oversight from [name]. Training will emphasize the protection of human subjects and confidentiality, the role of gender norms in patient-provider relationships, managing group dynamics, facilitating transformative dialogues without creating conflict, and identifying and minimizing adverse outcomes.

Statistical Analysis Plan

To evaluate the time by intervention effect on primary and secondary outcomes, we used Generalized Estimating Equations (GEE) in SPSS v. 28, which can account for dependency in the data related to the clinic clusters and repeated measures. First, we used GEE to examine baseline equivalence between treatment arms in both HIV care provider and client cohorts. We tested variables that differed at a level of p < 0.10 between treatment arms as covariates in the models testing intervention effect; only variables significant at p < 0.05 and/or making a difference in the intervention effect were maintained in the final models. We report the time by arm interaction. For all provider and client analyses, we tested the time by intervention by gender effect. For providers, we also tested the time by intervention by cadre effect, categorizing providers into certified health workers (licensed doctors, nurses, counselors) vs. lay health workers or non-specialized staff (e.g., peers). These interactions are only presented if they were statistically significant (p < 0.05). We report unstandardized betas (b) and standard errors (SE) for continuous outcomes and odds ratios (ORs) and adjusted odds ratios (AORs) and 95% confidence intervals (CIs) for binary outcomes.

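### Criterion 3 pools patients whose viral load and adherence would change differently without training, and no ART-status-by-time term is named, so an uneven mix between arms can distort both time-by-arm effects

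*Combined protocol and SAP*

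**What the plan says.** Under Inclusion criteria, the patient outcomes include ART adherence and viral load, measured "by assessing 240 (60 per treatment facility, gender balanced) purposively sampled patients at baseline, 6-, and 12-month follow-up". Criterion 3 has several routes in:

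- pre-ART or recent starters: "pre-ART (newly diagnosed) or newly initiated on ART (within 1 year";
- struggling, by viral load: "most recent viral load results unsuppressed as assessed through clinic records";
- struggling, by adherence: "self-reported non-adherence as by the Adult AIDS Clinical Trials Group (AACTG) scale 4-day adherence recall questions".

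No quota or stratification by route is given. Under Recruitment & Sampling, the research assistant approaches patients non-randomly from a review of clinic records, and clinicians refer them: "After being referred by a clinician, our research assistant will inform individuals of the study and assess eligibility using an eligibility screening tool". Allocation is by clinic and comes before provider recruitment: "Once research staff are trained and our two clinics have been randomly assigned as intervention or control arm, we will recruit providers". (That sentence says two clinics; four are named elsewhere, and 4 x 60 = 240.) Provider consent is worded to hide the arm: "To mask the randomization of intervention and control, we will consent participants for participation in all aspects of the training".

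The Statistical Analysis Plan uses GEE and reports the time-by-arm interaction. Variables that differ between arms at p < 0.10 are tested as covariates, and are kept if significant at p < 0.05 and/or if they alter the intervention effect. The only other interactions named involve gender and, for providers, cadre. ART status is neither named nor excluded as a baseline variable, and the coding of pre-ART patients in the adherence model is not stated.

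**The concern.** A time-by-arm effect compares change between arms, so it is protected against a difference in starting level but not against a difference in expected change. Pre-ART patients have no ART adherence at baseline, and most would be expected to move from unsuppressed to suppressed once treated. Patients chosen for a poor viral load or poor adherence can regress towards the mean. Recent starters who are doing well have less room to change.

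With purposive sampling at four clinics, nothing in the design equalises these groups between arms. A covariate entered as a main effect shifts level and would generally leave different time trends in place. At stake is whether a viral-load or adherence result reflects the provider training or the kind of patient enrolled at each clinic.

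**Working it through.** **The plan's own figure.** 60 patients x 4 clinics = 240, so 120 per arm with two clinics per arm. The documents give no power calculation, ART-status mix or group-specific rates for patients. Every rate and mix below is an assumption.

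**Assumptions.** Viral load analysed as suppressed yes/no; baseline and one follow-up; no training effect in any group. Suppression: pre-ART 5% to 75%; on ART up to 1 year 60% to 80%; on ART longer 35% to 55%. The longer group is 50% of each arm, and the newer group is 50% minus the pre-ART share.

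**Formula.** With b and f the proportions suppressed at baseline and follow-up in an arm, the false time-by-arm odds ratio is [odds(f)/odds(b)] in the intervention arm divided by [odds(f)/odds(b)] in the control arm.

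**Worked case, pre-ART 20% vs 10%, all with a baseline viral load.**
- Intervention: b = 0.20 x 0.05 + 0.30 x 0.60 + 0.50 x 0.35 = 0.365; f = 0.20 x 0.75 + 0.30 x 0.80 + 0.50 x 0.55 = 0.665. Odds 0.575 and 1.985; ratio 3.45.
- Control: b = 0.10 x 0.05 + 0.40 x 0.60 + 0.50 x 0.35 = 0.420; f = 0.10 x 0.75 + 0.40 x 0.80 + 0.50 x 0.55 = 0.670. Odds 0.724 and 2.030; ratio 2.80.
- False odds ratio: 3.45 / 2.80 = 1.23.

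Logistic fits to expected cell frequencies give:

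| Pre-ART share, intervention/control (%) | 15/10 | 20/10 | 30/10 | 10/20 |
|---|---|---|---|---|
| All have a baseline viral load, unadjusted | 1.11 | 1.23 | 1.54 | 0.81 |
| Same, three-group main effect | 1.11 | 1.24 | 1.54 | 0.81 |
| Same, three-group x time | 1.00 | 1.00 | 1.00 | 1.00 |
| Half have one, unadjusted | 1.07 | 1.15 | 1.36 | 0.87 |
| None has one, unadjusted | 1.02 | 1.05 | 1.12 | 0.95 |

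In the last row a main effect gives 0.98 to 1.01. Over 729 sets of assumed rates, the first three columns range over 1.03-1.18, 1.07-1.40 and 1.16-2.03 if all have a baseline value, and 0.96-1.09, 0.92-1.19 and 0.86-1.48 if none has. The standard error of the log odds ratio is about 0.38, so the distortion is between ln(1.11)/0.38 = 0.27 and ln(1.54)/0.38 = 1.14 standard errors.

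**The p < 0.10 screen.** A simple test of pre-ART share by arm, ignoring clustering, flags 15/10, 20/10 and 30/10 about 32%, 70% and 99% of the time.

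**The two struggling routes.** Only one route selects on viral load. Hold pre-ART at 15% and newer at 35% in both arms, and split the longer group into viral-load-selected (5% to 40% suppressed) and adherence-selected (60% to 65%). With viral-load-selected shares of 30% vs 20%, the false odds ratio is 1.13 unadjusted and 1.17 with three-group x time. With 35% vs 15% it is 1.28 and 1.37. With sharper rates (2% to 45%, and 65% throughout) at 35% vs 15% it is 1.43 and 1.55. Keeping four groups x time gives 1.00.

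**Adherence.** If pre-ART patients are blank at baseline and 80% adherent at follow-up, with on-ART patients going from 60% to 65%, the four mixes give 1.03, 1.07, 1.15 and 0.93, and a main effect restores 1.00. Among on-ART patients alone, take the newer group at 75% to 78% and the longer group at 20-40% to 60%, with longer shares of 55% vs 45%. The false odds ratio is then 1.15 to 1.06 unadjusted, 1.17 to 1.07 with a main effect, and 1.00 with group x time.

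**The case against.** **The case rests on unknowns.** This stands. No document gives the mix by arm or says how many pre-ART patients have a baseline viral load. If none has, the central distortion is small. The largest central figure, 1.54, needs a 20-point gap and a baseline value for everyone.

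**The 1.00 after adjustment is built in.** This also stands: the data were generated from the groups later adjusted for. The split of the struggling group shows that a coarser grouping can leave the distortion or slightly enlarge it, which is why four levels are needed. Unmeasured differences within a level would remain.

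**Four clinics dominate the error rate.** A reader might infer that group x time restores a 5% false-positive rate. Simulations with patient-level standard errors and no clinic effect suggest so, but the SAP says its GEE accounts for clinic clusters. With a clinic-level sandwich on four clusters and a 1.96 cut-off, false positives are about 30% with or without the term when clinics are allocated at random. If both clinics with high pre-ART shares fall in one arm, the term lowers the rate from 36% to 30% at 20/10 and from 48% to 31% at 30/10. The SAP states no small-sample method, so no 5% claim should be made.

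**The SAP already adjusts.** In part. A reader might conclude that ART status would enter as a main effect only, but the text says only that variables were tested as covariates and gives no functional form. What can be said is that no covariate-by-time term is named.

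**Referral biased by arm.** Because clinics are allocated before providers are recruited and patients follow the provider assessment schedule, a reader might infer that clinicians who knew their arm chose different patients. The documents do not show this. The consent wording is meant to mask allocation, and the research assistant works from clinic records, so the choice is not the clinician's alone. Nor do they exclude it. The concern needs only an uneven mix, which chance across four clinics can produce.

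**Conclusion.** The point holds as a conditional weakness in the analysis. Criterion 3 pools groups with different expected trends, the sampling does not balance them, and the SAP names no term that would separate those trends from the training effect. If the mix differs between arms, the distortion can go either way. For pre-ART gaps of 5 to 20 points the central false odds ratio is 1.11 to 1.54 if all pre-ART patients have a baseline viral load, and 1.02 to 1.12 if none has. An uneven split between the two struggling routes, or between newer and longer-treated patients, can also distort the result with no pre-ART imbalance. These figures show what is possible under assumed rates, not that the trial's result is biased. Priority lies between worth considering and should be done, with medium confidence.

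**What to change.** Derive one mutually exclusive baseline group from the chart and baseline interview:

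1. pre-ART;
2. on ART up to 1 year;
3. on ART longer, last viral load unsuppressed;
4. on ART longer, not unsuppressed, self-reported non-adherence.

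Keep levels 3 and 4 apart. Tabulate the group by arm and clinic. Then, whatever the p < 0.10 screen shows:

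- Report beside the main result a viral-load model and an adherence model with group and group x time.
- Report the arm comparison at 6 and 12 months adjusted for group. Fix this in advance and do not trigger it by the observed baseline count. Some groups have little or no baseline variation by definition: with 24 or 48 pre-ART patients (10% or 20% of 240) at 5% suppressed, the chance that none is suppressed is 0.95^24 = 0.29 or 0.95^48 = 0.09.
- For adherence, restrict the baseline-to-follow-up contrast to patients on ART at baseline, and report pre-ART patients at follow-up only.

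The SAP is written in the past tense. If the analysis is complete, label all of this as sensitivity analysis.

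Cost: SAP wording, a few model terms, and the ART start date, which is not among the example chart items, although charts are reviewed again at each visit. The field should not depend on screening answers: Recruitment & Sampling says "No identifying information will be recorded during the eligibility screening", while the baseline patient assessment text says nothing is recorded at that stage. The standard error of the log odds ratio for viral load rises from about 0.38 to about 0.44-0.46 with four-group x time. The follow-up-only comparison gives up the subtraction of baseline differences between clinics, so it supplements the change model and does not replace it. None of this addresses inference with four clusters.
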